17. PREVIOUS RESPIMAT® SMI USE

Analysis Set: FAS

Information on previous Respimat® use collected on the “Prior Respimat® Use” eCRF page will be summarised for Respimat® SMI-experienced patients cohort subgroups.

For *Respimat® SMI-experienced patients on maintenance treatment with a re-usable Respimat® SMI at study entry* the following will be described:

- Re-usable Respimat® SMI product prescribed prior to study entry: Spiriva®, Striverdi®, Spiolto®.
- By overall and type of re-usable Respimat® SMI product prescribed prior to study entry:
 - Duration of re-usable Respimat® SMI product prescribed prior to study entry (days) - calculated relative to signed ICF date.

For *Respimat® SMI-experienced patients on maintenance treatment with a disposable Respimat and switching to a re-usable Respimat® SMI at study entry* the following will be described:

Document:	\	.net\Enterprise\Sites\USCBG\Depts\BioStat\Boehringer\Documentation\SAP\Final	
Author:		Version Number:	1.0

Template No.: RWI_TP_BIOS0013 Revision 1

Reference: RWI_WI_BIOS0015

Effective Date: 15Jun2018

- Disposable Respimat® SMI product prescribed prior to study entry: Spiriva®, Striverdi®, Spiolto®.
- By overall and type of disposable Respimat® SMI product prescribed prior to study entry:
 - Duration of disposable Respimat® SMI product prescribed prior to study entry (days) - calculated relative to date of last use of disposable Respimat® SMI product.

Derivations:

- For *Respimat® SMI-experienced patients on maintenance treatment with a re-usable Respimat® SMI at study entry:*
 - *Duration of re-usable Respimat® SMI product prescribed prior to study entry (days) = [(date of signed ICF – date of first use of re-usable Respimat® SMI) + 1].*
- For *Respimat® SMI-experienced patients on maintenance treatment with a disposable Respimat and switching to a re-usable Respimat® SMI at study entry:*
 - *Duration of disposable Respimat® SMI product prescribed prior to study entry (days) = [(date of last use of disposable Respimat® SMI – date of first use of disposable Respimat® SMI) + 1].*

Details on conversion factors used for dates and on handling of partial dates of first and last use of re-usable Respimat® SMI are described in [Appendix 1](#) and [Appendix 2](#), respectively.

Supportive listing for previous Respimat® SMI use will be provided.

Document:	\	.net\Enterprise\Sites\USCBG\Depts\BioStat\Boehringer\Documentation\SAP\Final	
Author:		Version Number:	1.0

Template No.: RWI_TP_BIOS0013 Revision 1

Reference: RWI_WI_BIOS0015

Effective Date: 15Jun2018

18. PREVIOUS NON-RESPIMAT® SMI MAINTENANCE PRODUCT USE

Analysis Set: FAS

Information on previous non-Respimat® maintenance product use in the 6 months prior to study entry will be collected on the “Prior & Current COPD & Non-COPD Medications”/“Prior & Current COPD & Non-COPD Medications Details” eCRF pages.

Non-Respimat® SMI maintenance product is defined as a related COPD inhaler other than Respimat® SMI products which was given for maintenance treatment. Some of non-Respimat® SMI maintenance products that will be considered in this study and the correspondent type of inhaler devices are described in [Table 4](#). Other non-Respimat® SMI maintenance products identified prior to the DBL that are not presented in [Table 4](#) will also be considered in the final analysis.

Document:	\	.net\Enterprise\Sites\USCBG\Depts\BioStat\Boehringer\Documentation\SAP\Final
Author:		Version Number: 1.0

Template No.: RWI_TP_BIOS0013 Revision 1 Reference: RWI_WI_BIOS0015

Effective Date: 15Jun2018

Table 4 Non-Respimat® SMI maintenance products and type of inhaler devices

Medication	Pharmacological class	Inhaler type
Oxeze®/Oxis® Turbuhaler (formoterol)	LABA	DPI
Foradil® Aerolizer (formoterol)	LABA	DPI
Hirobriz®/Onbrez®/Oslif® Breezhaler (indacaterol)	LABA	DPI
Serevent®/Dilamax®/Ultrabeta® Diskus (salmeterol)	LABA	DPI
Atimos® (formoterol)	LABA	MDI
Serevent®/Dilamax®/Salmeterol Neolab®/Ultrabeta® (salmeterol)	LABA	MDI
Seebri®/Tovanor® Breezhaler (glycopyrronium)	LAMA	DPI
Spiriva®/Braltus®/Grgal® Handihaler (tiotropium)	LAMA	DPI
Bretaris®/Eklira® Genuair (aclidinium)	LAMA	DPI
Incruse® Ellipta (umeclidinium)	LAMA	DPI
Anoro®/Laventair® Ellipta (umeclidinium plus vilanterol)	LAMA + LABA	DPI
Brimica®/Duaklir® Genuair (aclidinium plus formoterol)	LAMA + LABA	DPI
Ultibro®/Xoterna® Breezhaler (glycopyrronium plus indacaterol)	LAMA + LABA	DPI
Bevespi® Aerosphere (glycopyrronium plus formoterol)	LAMA + LABA	MDI
Symbicort®/Assieme® Turbuhaler (budesonide plus formoterol)	ICS + LABA	DPI
DuoResp®/BiResp® Spiromax (budesonide plus formoterol)	ICS + LABA	DPI
Bufomix®/Gibiter® Easyhaler (budesonide plus formoterol)	ICS + LABA	DPI
Seretide®/Brisomax®/Maizar®/Veraspir® Diskus (fluticasone propionate plus salmeterol)	ICS + LABA	DPI
Aerivio®/Airexar® Spiromax (fluticasone propionate plus salmeterol)	ICS + LABA	DPI
AirFluSal® ForSpiro (fluticasone propionate plus salmeterol)	ICS + LABA	DPI
Breo®/Relvar®/Revinty® Ellipta (fluticasone furoate plus vilanterol)	ICS + LABA	DPI
Symbicort® Rapihaler (budesonide plus formoterol)	ICS + LABA	MDI
Flutiform® MDI (fluticasone propionate plus formoterol)	ICS + LABA	MDI
Seretide®/Serkep® MDI (fluticasone propionate plus salmeterol)	ICS + LABA	MDI
Trelegy® Ellipta (fluticasone furoate plus umeclidinium bromide plus vilanterol trifenate)	ICS+LAMA+LABA	DPI
Trimbow® (Beclometasone plus formoterol plus glycopyrronium)	ICS+LAMA+LABA	MDI

DPI: Dry powder inhaler; ICS: Inhaled corticosteroids; LABA: Long-acting beta₂-agonists; LAMA: Long-acting muscarinic antagonists; MDI: Metered dose inhaler.

The following will be summarised:

Document: \\ .net\Enterprise\Sites\USCBG\Depts\BioStat\Boehringer\Documentation\SAP\Final

Author:

Version Number:

1.0

Version Date:

100CT2019

Template No.: RWI_TP_BIOS0013 Revision 1

Reference: RWI_WI_BIOS0015

Effective Date: 15Jun2018

- Non-Respimat® SMI maintenance products prescribed prior to study entry:
 - Long-acting beta₂-agonists (LABA): refer to “Medication” column in [Table 4](#) for LABA Pharmacological class.
 - Long-acting muscarinic antagonists (LAMA): refer to “Medication” column in [Table 4](#) for LAMA Pharmacological class.
 - LAMA + LABA: refer to “Medication” column in [Table 4](#) for LAMA+LABA Pharmacological class.
 - Inhaled corticosteroids (ICS) + LABA: refer to “Medication” column in [Table 4](#) for ICS+LABA Pharmacological class.
 - ICS+LAMA+LABA: refer to “Medication” column in [Table 4](#) for ICS+LAMA+LABA Pharmacological class.
- By non-Respimat® SMI maintenance products prescribed prior to study entry:
 - Duration of non-Respimat® SMI maintenance product prescribed prior to study entry (days) - calculated relative to end date.

In case of a patient reports more than one period of treatment exposure for a given maintenance product, the duration will be the sum of all the periods (excluding the time without treatment between periods).

- Inhaler device used prior to study entry (by pharmacological class and medication): DPI, MDI, Both (DPI+MDI), None.
- Last non-Respimat® SMI maintenance product prescribed prior to study entry: refer to “Medication” column in [Table 4](#), None.
- Last inhaler device used prior to study entry: DPI, MDI, None.

Derivations:

Document: \\ .net\Enterprise\Sites\USCBG\Depts\BioStat\Boehringer\Documentation\SAP\Final

Author:

Version Number:

1.0

Version Date:

100CT2019

Template No.: RWI_TP_BIOS0013 Revision 1

Reference: RWI_WI_BIOS0015

Effective Date: 15Jun2018

- *Duration of non-Respimat® SMI maintenance product prescribed prior to study entry (days) = [(End date – Start date) + 1].*
- *Last non-Respimat® SMI maintenance product prescribed prior to study entry = non-Respimat® maintenance product prescribed prior to study entry where max (Start date) < date of signed ICF and End date < date of signed ICF.*
- *Last inhaler device used prior to study entry = inhaler device associated with the last non-Respimat® SMI maintenance product prescribed prior to study entry.*

Details on conversion factors used for dates and on handling of partial dates of start and end date of medications are described in [Appendix 1](#) and [Appendix 2](#), respectively.

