Pulmonary function (based on most recent spirometry test in the 12 months prior to study entry ¹) (if available)	X	
Disease severity based on 2019 GOLD grade and group ²	X	
Respimat® SMI product prescribed (Spiriva®, Striverdi® or Spiolto®)	X	
Duration of treatment with disposable Respimat® SMI ³	X	
Last day of use of disposable Respimat® SMI ³	X	
Date of first prescription of re-usable Respimat® SMI	X	
Number of COPD exacerbations (in the 12 months prior to study entry) and during the study period	X	X

Document: \\ .net\Enterprise\Sites\USCBG\Depts\BioStat\Boehringer\Documentation\SAP\Final

Author: Version Number: 1.0

Version Date: 100CT2019

Template No.: RWI_TP_BIOS0013 Revision 1

Reference: RWI_WI_BIOS0015

Effective Date: 15Jun2018

	Study entry (Baseline)	Follow-up assessment (4-6 weeks after baseline)
COPD-related concomitant medications (in the 6 months prior to study entry and during the study period ⁴)	X	X
Comorbidities	X	X
Smoking status / history	X	X
PASAPQ completed by the patient ⁵	X	X
Respimat® SMI type used during study period (disposable or re-usable)		X
Questions on the ease of handling of re-usable Respimat® SMI		X
Question on Respimat® SMI preference (disposable vs re-usable) ⁵		X
Safety: Serious and non-serious ADRs, AEs with a fatal outcome, and other reportable safety events		X
Details of discontinuation of the re-usable Respimat® SMI during the study period ⁴ (if applicable)		X

¹ If more than one measurement is available in the 12-month period prior to study entry, the measurement closest to the study entry will be included.

² GOLD patient group (A, B, C or D) will be appraised based on available exacerbation history, assessment of symptoms based on CAT, and GOLD grade (1-4) spirometry classification of airflow limitation based on post-bronchodilator spirometry results, if available (GOLD 2019 [1]).

³ This will be assessed in Respimat® SMI-experienced patients only.

⁴ The study period starts with the baseline visit and ends with the follow-up assessment, which is approximately 4-6 weeks.

⁵ PASAPQ at study enrolment (baseline visit) and the question on Respimat® SMI preference (disposable vs re-usable) will be administered only to the Respimat® SMI-experienced patients switching from disposable to re-usable Respimat® SMI at the time of study entry.

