8.4 Baseline Visit

The routine visit, at which a patient is enrolled in the study (time of ICF signature), will be treated as the baseline (study entry) visit.

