9.4 Examination of Subgroups

Subgroup analyses (in case of more than 20% of patients included in the FAS) will be conducted on primary and secondary outcomes based on the subgroups as defined below (some categories may be grouped when needed). The subgroup analyses will not be performed on any subgroup category “Missing”, “Unknown”, “None” or “Not Assessed”. All the subgroup analyses will be exploratory.

The following subgroups will be defined:

- Age:
 - ≥ 40 to < 65 years.
 - ≥ 65 to < 75 years.
 - ≥ 75 years.
- Global Initiative for Chronic Obstructive Lung Disease (GOLD) patient group:
 - A (less symptoms / low risk).
 - B (more symptoms / low risk).
 - C (less symptoms / higher risk).
 - D (more symptoms / higher risk).

Document: \\ .net\Enterprise\Sites\USCBG\Depts\BioStat\Boehringer\Documentation\SAP\Final

Author: Version Number: 1.0
Version Date: 100CT2019

Template No.: RWI_TP_BIOS0013 Revision 1

Reference: RWI_WI_BIOS0015

Effective Date: 15Jun2018

- GOLD grade:
 - 1 (Mild).
 - 2 (Moderate).
 - 3 (Severe).
 - 4 (Very Severe).
- Smoking status:
 - Current.
 - Former.
 - Never.
- Type of re-usable Respimat® SMI product prescribed at study entry:
 - Spiriva® 2.5 µg inhalation solution.
 - Striverdi® 2.5 µg inhalation solution.
 - Spiolto® 2.5 µg / 2.5 µg inhalation solution.
- For Respimat® SMI-naïve patients, last non-Respimat® SMI maintenance product prescribed prior to study entry: refer to “Medication” column in [Table 4](#).
- For Respimat® SMI-naïve patients, last inhaler device used prior to study entry:
 - Dry powder inhaler (DPI).
 - Metered dose inhaler (MDI).

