16. PREVIOUS AND CONCOMITANT MEDICATIONS

Analysis Set: FAS

Concomitant medications are medications which started prior to the study entry (date of signed ICF) and continued during the study period, as well as those that started during the study period. Any medication without the start and end date will also be considered as concomitant. Previous medications are those medications which were started and stopped in the 6 months prior to study entry.

Previous and concomitant medications will be coded using the most current available version of World Health Organization Drug Dictionary (WHO-DD) B3 Format at the time of DBL and will be analysed overall and by patient cohort regarding COPD-related status from the “Prior & Current COPD & Non-COPD Medications”/“Prior & Current COPD & Non-COPD Medications Details” eCRF pages.

Previous and concomitant medications will be summarised as the number and percentage of patients by PT. Each patient will be counted only once within a given PT. Previous and Document: \\ .net\Enterprise\Sites\USCBG\Depts\BioStat\Boehringer\Documentation\SAP\Final

Author: Version Number: 1.0
Version Date: 100CT2019

Template No.: RWI_TP_BIOS0013 Revision 1

Reference: RWI_WI_BIOS0015

Effective Date: 15Jun2018

concomitant medications will be displayed in terms of frequency tables sorted on decreasing frequency of PT. In case of equal frequency regarding PT, alphabetical order will be used.

A supportive listing for previous and concomitant medications taken previously and during the study period will be provided.

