- If the date is completely missing, no imputation will be performed.

Incomplete and partial dates for date of first use and date of last use of disposable Respimat® SMI prior to study entry will be imputed as follows:

- If the day of first use of disposable Respimat® SMI date is missing, it will be imputed to the 15th day of the month.

Document: \\ .net\Enterprise\Sites\USCBG\Depts\BioStat\Boehringer\Documentation\SAP\Final

Author: Version Number: 1.0

Version Date: 100CT2019

Template No.: RWI_TP_BIOS0013 Revision 1

Reference: RWI_WI_BIOS0015

Effective Date: 15Jun2018

- If both day and month of first use of disposable Respimat® SMI date are missing but the first use year is prior to the year of the signed ICF date, the month and day will be imputed as July 1st.
- If both day and month of first use of disposable Respimat® SMI date are missing but the first use year is equal to the year of the signed ICF date, the month and day will be imputed as January 1st.
- If the disposable Respimat® SMI first use date is completely missing, no imputation will be performed.
- Incomplete disposable Respimat® SMI last use date will be replaced by the last day of the month (if day is missing only).
- If the disposable Respimat® SMI last use date is completely missing, it will be imputed by the signed ICF date.

Incomplete and partial dates for prescribed date of re-usable Respimat® SMI at study entry will be imputed as follows:

- If the day of prescribed date of re-usable Respimat® SMI at study entry is missing, but the month and year are equal to the dispensed date, then the prescribed date will be replaced by the dispensed date.
- If both day and month of prescribed date of re-usable Respimat® SMI at study entry are missing but the prescribed year is equal to the year of the dispensed date, then the prescribed date will be replaced by the dispensed date.
- In all other cases, the missing day of the prescribed date of re-usable Respimat® SMI at study entry will be replaced by 1.

Document: \\ .net\Enterprise\Sites\USCBG\Depts\BioStat\Boehringer\Documentation\SAP\Final

Author: Version Number: 1.0

Version Date: 100CT2019

Template No.: RWI_TP_BIOS0013 Revision 1

Reference: RWI_WI_BIOS0015

Effective Date: 15Jun2018

- If the prescribed date is missing, it will be imputed by the dispensed date. If the dispensed date is missing, prescribed date will be imputed by the signed ICF date.

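### Two SAP date rules give wrong values as written: a start imputed after a known stop makes durations zero or negative, and an inhaler stopped on the entry day cannot be the 'last' prior product or device

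*SAP*

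**What the plan says.** **Last product and device.** SAP 18 takes as last the product "where max (Start date) < date of signed ICF and End date < date of signed ICF"; the last device is the one belonging to that product. Study entry is the visit "at which a patient is enrolled in the study (time of ICF signature), will be treated as the baseline (study entry) visit" (SAP 8.4), so the ICF (consent) date is the entry date.

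**Use.** SAP 9.4 makes both variables subgroups for the primary and secondary outcomes in naïve patients, the device one being labelled "For Respimat® SMI-naïve patients, last inhaler device used prior to study entry". The same section says "The subgroup analyses will not be performed on any subgroup category" recorded as 'None', among other labels. It runs a subgroup only if it holds more than 20% of the full analysis set (FAS).

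**Duration.** SAP 18 defines it as end date minus start date plus one, sums it over separate periods of the same product, and refers to Appendix 2 for partial dates.

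**Imputation.** Under the medication rules of Appendix 2, a start goes to the ICF date in three cases: wholly missing; day missing in the ICF month; day and month missing in the ICF year. Other partial starts have the missing part set to 1. A stop lacking only its day goes to month-end, limited only by a date of death. No rule compares an imputed start with a known stop.

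**The concern.** An imputed date should not contradict a recorded one. Someone whose earlier inhaler has a recorded stop in May cannot have started it in October, yet that is what the start rule produces. The impossible duration enters the SAP 18 table, or is silently subtracted when periods are added. The product also fails the start condition, so it drops out of contention for 'last'.

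The end-date condition has a separate fault. A naïve patient may well use the old inhaler until the visit at which the re-usable Respimat is prescribed. That inhaler was prescribed and used before entry, which is what the variable's label asks for, but a recorded stop on the visit date disqualifies it.

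At stake are the SAP 18 descriptive tables and the last-product and last-device subgroups.

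**Working it through.** The plan states no numerical result on this point, so there is no figure to reproduce. I applied the rules as written. The ICF date of 15 October 2019 is an assumption for illustration; the enrolment window (September to December 2019) is from SAP 4.1.

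**1. Duration when the start is set to the ICF date.** For a known stop k days before the ICF date:

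duration = (ICF − k) − ICF + 1 = 1 − k

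This is 0 for k = 1 and negative for k ≥ 2, whatever the ICF date.

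| Recorded start | Known stop | Imputed start | Duration as written | Possible true duration |
|---|---|---|---|---|
| missing | 31 May 2019 (k = 137) | 15 Oct 2019 | 1 − 137 = −136 | at least 1 |
| 2019 | 30 Jun 2019 (k = 107) | 15 Oct 2019 | 1 − 107 = −106 | 1 to 181 |
| Oct 2019 | 10 Oct 2019 (k = 5) | 15 Oct 2019 | 1 − 5 = −4 | 1 to 10 |
| 2018 | 31 May 2019 | 1 Jan 2018 | 365 + 151 = 516 | 152 to 516 |

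The last row is a contrast: a prior-year start is handled sensibly. In the first three rows the start equals the ICF date, so the product also fails the start condition in SAP 18.

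**2. Summed periods.** One period runs from 1 January to 31 May 2019 (151 days). A second has start '2019' and stop 31 August (k = 45, so 1 − 45 = −44). The total as written is 151 − 44 = 107 days. If the second period followed the first, it lasted 1 to 92 days (1 June to 31 August at most), so the true total is 152 to 243.

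**3. Reach over the enrolment window.** There are 30 + 31 + 30 + 31 = 122 possible ICF dates. The six-month look-back begins between 1 March and 30 June 2019, always inside the ICF year, so every year-only start within it goes to the ICF date. Pairing each ICF date with each earlier stop in its look-back gives 22,388 pairs, all with durations from −183 to 0. This shows that the fault does not depend on the chosen date; it does not count patients.

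**4. Stop on the entry day.** A product started on 1 May qualifies as last if stopped on 14 October (167 days) but not if stopped on 15 October (168 days). Give the patient an MDI from 1 to 30 April and a DPI from 1 May to 15 October: the rule returns the MDI. Remove the MDI and it returns 'None'.

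**5. Stop in the ICF month, day missing.** Month-end is never before the ICF date, so such a product fails on all 122 dates. Not all of these are errors. The possible ICF-date and stop-day combinations number 30² + 31² + 30² + 31² = 3,722. Those with the stop after entry number 435 + 465 + 435 + 465 = 1,800 (30 × 29 / 2 = 435; 31 × 30 / 2 = 465). That is 1,800 / 3,722 = 48%.

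**6. Subgroup threshold.** If the FAS is about 250, a category needs more than 0.20 × 250 = 50 patients. At least half of the patients are expected to be Respimat-experienced (Protocol 9.1), so naïve patients number about 125 at most, and a category must hold over 50 / 125 = 40% of them. SAP Table 4 lists 26 product entries. Realistically only the DPI/MDI split or grouped products can qualify.

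**The case against.** **The end-date rule is a definition.** SAP Table 1 states that "The study period starts with the baseline visit and ends with the follow-up assessment", so an inhaler stopped that day overlaps the study period, and a strict inequality keeps prior and on-study products apart. That is a coherent aim, but it does not suit a variable labelled as last used before entry: overlapping by a day does not make an older inhaler, or none, the last one.

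**The SAP does not contradict itself on the entry day.** For the disposable inhaler, Appendix 2 says "If the disposable Respimat® SMI last use date is completely missing, it will be imputed by the signed ICF date". A reader might infer a direct conflict with SAP 18. There is none: that rule concerns another cohort and feeds a duration, not the choice of a product. It shows only that the SAP accepts the entry day as a possible last day of a prior inhaler.

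**The SAP 16 tables may be unaffected.** SAP 16 counts as concomitant the medicines that started before entry and "continued during the study period, as well as those that started during the study period", and adds: "Previous medications are those medications which were started and stopped in the 6 months prior to study entry". A reader might infer that a medicine with a start imputed to the ICF date is always tabulated as concomitant. SAP 16 does not refer to Appendix 2, and its separate provision for medicines lacking both dates would be largely redundant if imputed dates were used. The effect follows only if classification uses imputed dates, which is not stated.

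**Detection.** Derived variables based on imputed values are flagged in listings (SAP 9.3), SAP 5.2 plans a dry run and a data review meeting, and Protocol 9.6 describes edit checks for illogical data. A negative duration may well be seen. A flag could prompt review of a summed total such as 107, but the value itself looks ordinary; a 'None' caused by complete dates carries no imputation flag.

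**Conclusion.** Both faults follow from the text, and no other section corrects them. The start rule gives 1 − k days for a stop k days before consent, and the end-date rule loses an inhaler stopped at the entry visit. Imputing a start to the ICF date is reasonable when the stop is unknown or after entry; the fault lies in applying it against a known earlier stop.

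The impact is minor. It covers the descriptive SAP 18 tables and exploratory subgroups that few categories can be large enough to enter. A reader might infer bias in the main results. The documents do not support that: the overall and cohort PASAPQ means and the paired test use neither variable. Nor is every consent-month stop with a missing day misclassified, since about half of the possible days fall after entry, where exclusion is what SAP 18 intends. The documents do not say how often partial dates or entry-day stops occur, so the number of patients affected cannot be given. The numerical examples rest on an assumed ICF date; the sign of the result does not.

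**What to change.** **Appendix 2, medications**

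- Never impute a start later than a known stop.
- For a known stop on or before the ICF date, apply the existing rule that sets a missing day or month to 1, but no earlier than the day after a preceding recorded period of the same product. Flag the duration as an imputed upper bound. The summed example then gives 151 + 92 = 243 days; without the no-overlap limit it would give 151 + 243 = 394, counting the first period twice. Appendix 2 already uses 1 January for same-year partial dates of diagnosis, spirometry and first Respimat use.
- For a wholly missing start with a known stop on or before the ICF date, leave the duration missing and let the product qualify as last by its stop date. If the stop is before the ICF date, also state in SAP 16 that the medicine is previous.

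**SAP 18**

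- Change the end-date condition to on or before the ICF date.
- For a stop in the ICF month with the day missing, query the site. If it stays unresolved, flag the last product or device as uncertain. Do not set it to 'None', and do not cap it automatically at the ICF date, which would exchange one misclassification for another.

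**Cost.** A little SAP wording and programming before database lock, plus some site queries. Some durations become missing or flagged upper bounds, which look more plausible than a negative number, so the flag matters.

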4. STUDY DESIGN

4.1 General Description

This is a multicentre, open-label, prospective, real-world non-interventional study of patients with COPD, prescribed with re-usable Respimat® SMI. Patient enrolment will commence in September 2019 and is expected to end in December 2019. The last patient last assessment is expected in February 2020 (see Section 6 of the Clinical Study Protocol [CSP] for details of study milestones).

For this study, two patient cohorts will be defined according to the prescription of a Respimat® SMI product:

- 1) Respimat® SMI-experienced, defined as patients who have been on maintenance treatment with a Respimat® SMI product (Spiriva®, Striverdi® or Spiolto®) and receive a refill prescription at study entry. This patient cohort will further be divided into two subgroups:
 - 1a) Patients on maintenance treatment with a re-usable Respimat® SMI at study entry.
 - 1b) Patients on maintenance treatment with a disposable Respimat® SMI and switching to a re-usable Respimat® SMI at study entry.
- 2) Respimat® SMI-naïve, defined as patients who have not previously used a Respimat® SMI product and receive their first prescription at study entry.

The prescription at study entry for both patient cohorts should be for a re-usable Respimat® SMI product.

Document:	\	.net\Enterprise\Sites\USCBG\Depts\BioStat\Boehringer\Documentation\SAP\Final
Author:		Version Number: 1.0

Template No.: RWI_TP_BIOS0013 Revision 1

Reference: RWI_WI_BIOS0015

Effective Date: 15Jun2018

The study population will be identified by the participating physicians involved in the diagnosis, treatment and management of COPD patients (general practitioners and/or specialist physicians including pneumologists). Eligible patients must be prescribed and use a re-usable Respimat® SMI product (as per the routine clinical practice of the participant sites) after being prescribed a Respimat® SMI product for the first time in the course of standard clinical practice (Respimat® SMI-naïve patients) or after having switched from a disposable Respimat® SMI (Respimat® SMI-experienced patients).

[figure not shown]

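### SAP 18 derives the last prior inhaler only from products ended before consent, ordered by start date, so Respimat-naïve patients still using a maintenance inhaler at entry become 'None' or get an older product in two exploratory subgroups

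*SAP*

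**What the plan says.** SAP 18 (Derivations) selects the last product as the one "where max (Start date) < date of signed ICF and End date < date of signed ICF". The device variable is then the "inhaler device associated with the last non-Respimat® SMI maintenance product prescribed prior to study entry". The output row reads "Last inhaler device used prior to study entry: DPI, MDI, None".

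SAP 9.4 uses both variables as subgroups for the primary and secondary outcomes in the naïve cohort, the device one being worded "For Respimat® SMI-naïve patients, last inhaler device used prior to study entry". A subgroup must hold more than 20% of the FAS, all subgroup analyses are exploratory, and "The subgroup analyses will not be performed on any subgroup category" that is labelled as missing, unknown, none or not assessed.

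Three other places bear on the rule:

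- SAP 4.1 makes a patient naïve with respect to Respimat only: "defined as patients who have not previously used a Respimat® SMI product and receive their first prescription at study entry". The eligibility criteria (Protocol 9.2.3) do not exclude users of other maintenance inhalers.
- SAP 8.4 ties entry to consent: the routine visit "at which a patient is enrolled in the study (time of ICF signature), will be treated as the baseline (study entry) visit".
- SAP 16 expects treatments that run through entry: "Concomitant medications are medications which started prior to the study entry (date of signed ICF) and continued during the study period".

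Appendix 2 imputes a medication stop date only when the day alone is missing, using month end (or the date of death, if earlier). Otherwise the stop date stays incomplete. A wholly missing start date is set to the consent date.

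**The concern.** The labels refer to the last product prescribed and the last device used before entry. The rule answers a narrower question: among products already finished before the consent date, which one started latest?

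An inhaler continued past the visit has a blank or later end date and can never be chosen. One whose end is recorded on the visit date also fails, because the inequality is strict. Relaxing the inequality would rescue only that second group. Separately, ordering by start date ignores which product was in use most recently.

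At stake is who enters the two naïve-cohort subgroups. Patients on an inhaler at entry are left out or filed under an older product. In the descriptive table they share the 'None' row with patients who had no prior inhaler. The neighbouring duration row (end minus start plus one) has the same weakness: it cannot be computed for an ongoing product, and it counts days after consent for one stopped later.

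**Working it through.** The plan states no figure for this derivation, so the check applies the rule to constructed histories and then does the arithmetic on the 20% threshold.

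**1. The rule on test patients.** Consent (ICF) date is 15 Oct 2019. The wording allows two readings. A: keep products with start and end before consent, then take the latest start. B: take the latest start before consent, then require that product to have ended. A blank end date is treated as failing the end condition.

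| History | A | B | Device used last |
|---|---|---|---|
| DPI from 1 Jan 2018, ongoing | None | None | DPI |
| Same DPI, ended 15 Oct 2019 | None | None | DPI |
| Same DPI, ended 22 Oct 2019 | None | None | DPI |
| MDI 20 Apr–30 Jun 2019; DPI from 1 Jul, ongoing | MDI | None | DPI |
| One DPI 20 Apr–30 Jun 2019; another DPI from 1 Jul, ongoing | DPI (older product) | None | DPI |
| DPI 1 Jan 2018–30 Sep 2019; MDI 1 May–30 Jun 2019 | MDI | MDI | DPI |
| DPI stopped Oct 2019, day missing (imputed 31 Oct) | None | None | DPI |
| DPI start wholly missing (imputed 15 Oct), ended 1 Oct | None | None | DPI |
| DPI ended 14 Oct 2019 | DPI | DPI | DPI |
| No product | None | None | None |

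The problem with inhalers in use at entry appears under both readings. An older product is substituted only under A, and the device is then wrong only if the two device types differ. The ordering problem needs overlap: a later-started product must stop before an earlier-started one. For strictly sequential stopped products, latest start and latest use agree.

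**2. The threshold.** Inputs: 250 patients (Protocol 9.5, SAP 6); at least half expected to be experienced (Protocol 9.1), so about 125 naïve at most; FAS taken as all 250.

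- 20% of 250 is 50, and more than 20% means at least 51.
- 51/125 = 40.8% of the naïve cohort must fall in one category.
- DPI and MDI can both qualify only if 2 × 51 = 102 patients are classifiable.

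**3. Upper bound on the loss.** Let c be the share of naïve patients with a continuing inhaler and no older stopped product. The documents do not give c. If every naïve patient had a prior inhaler, 125 × (1 − c) remain classifiable:

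| c | Classifiable | Possible at the threshold |
|---|---|---|
| 0 | 125 | both devices |
| 20% | 100 | at most one |
| 40% | 75 | at most one |
| 60% | 50 | none |

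Even with everyone on one device type, the category fails once the loss exceeds 1 − 51/125 = 59.2%.

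**4. Practice elsewhere in the SAP.** SAP 17 ends the prior duration of ongoing re-usable Respimat use at the consent date. Appendix 2 sets a wholly missing last-use date for the disposable device to the consent date. SAP 18 has no such cap.

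**The case against.** The restriction may be deliberate. SAP 18 is headed as previous use, and SAP 16 separates previous medications (started and stopped before entry) from concomitant ones. Continuing inhalers are still summarised under SAP 16, and the SAP 18 row for any prior device has no end-date condition. This explains the end-date filter in part. It does not fit a variable labelled as the last device used before entry, does not explain ordering by start date, and does not return these patients to the subgroups. For the product variable, labelled by prescription, start date is a more defensible order.

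The threshold also restricts these analyses whatever the derivation. Table 4 lists 26 product rows, and 51 patients on one of them is unlikely without grouping, which SAP 9.4 permits. A two-device display needs at least 102 of 125 classifiable. That stands and limits what a correction can gain.

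A reader might infer that a planned DPI-versus-MDI comparison fails. SAP 9.4 states none: it lists categories within which outcomes are examined, and Protocol section 4 says only that subgroup analyses may be done. A reader might also take 100, 75 and 50 as expected counts. They are not. Some naïve patients will have had no prior inhaler, and under reading A continuing users with an older stopped product stay classified, though possibly wrongly.

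Capping at consent has a consequence of its own: a retained inhaler outranks one stopped shortly before entry. That follows from the wording about last use, but the SAP should say so.

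**Conclusion.** The point holds, with limited reach. As written, the rule cannot select an inhaler still in use at entry, and with overlapping stopped products it can select one that was not used last. It affects two exploratory naïve-cohort subgroup variables and the descriptive prior-duration row. The primary estimate and the paired comparison in switchers are untouched, and the documents do not support reading this as a threat to either.

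The size is unknown because the share of naïve patients with a continuing inhaler is not given. The loss to 100, 75 or 50 classifiable patients is an upper bound. It assumes 125 naïve patients in a FAS of 250, a prior inhaler for all of them, and no older stopped product for those continuing. A wrong device, rather than only a wrong product, requires the device types to differ. The correction is worth making before database lock because it uses dates the eCRF already collects.

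**What to change.** Replace the SAP 18 derivation as follows:

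- Among non-Respimat maintenance products started before the consent date, set prior end = min(End date, ICF date). Set products recorded as ongoing to the ICF date.
- The last product is the one with the latest prior end; ties go to the latest start. The last device follows from it, except that a DPI and an MDI both in use at entry are shown as 'Both'.
- A wholly missing start date imputed to the ICF date must not exclude a product recorded as prior. Its duration should be left missing.
- Treat a stop date that is unknown, as distinct from ongoing, as missing.
- Keep 'None' for patients with no maintenance inhaler in the 6 months before entry.
- Compute prior duration as prior end − Start date + 1, for each period where a product has several.

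On the test patients in the table, ordering by last use up to consent returns the device used last in every case and leaves 'None' only for the patient with no product.

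The cost is a short SAP amendment and a few lines of programming. It assumes that the medication page distinguishes ongoing from unknown stop dates, which the documents do not show. 'Both' already exists for the any-prior-device row but is new to the last-device variable, and it slightly lowers the DPI and MDI counts against the 20% threshold.
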